15.5 Steps Taken to Control or Mitigate Risks

In-depth recommendations, special precautions and instructions regarding subject selection, device handling, physician training, device placement and system removal are included in the IFU. Mitigations and treatment for all adverse events will be performed per the current practice standards/standards of care as determined by the Investigator.

Device Design

The HM3 has several features to mitigate the risks to the patients including, but not limited to the following:

- Alarms audibly and visibly indicate problems, such as low flow, to the patients, when appropriate. The alarms are also modulated in duration depending on the severity of the problem (Hazard vs. Advisory alarms).
- The power cables (i.e. driveline) have been designed to be difficult to unintentionally disconnect.
- The device was designed to be in compliance with international regulations on fire and shock hazards, biocompatibility, electromagnetic emissions and interference, and sterilization. These are outlined in the IFU.
- The IFU for the HM3 describes the validated implant technique.
- The LVAS is supplied with additional accessories to facilitate activities of daily living (e.g. shower bag) and the proper use of the device for different scenarios is explained in the IFU.
- The IFU has checklists of items that need to be checked periodically to ensure proper device function and to identify problems before they become critical.
- The HM3 LVAD has wide blood-flow paths and an artificial pulse feature to prevent stasis within the pump and thereby minimize the risk of thrombus formation.
- The HM3 LVAD has no mechanical bearings, which minimizes the damage to the components of the blood when flowing through the pump.
- The driveline cable was made modular via an inline connector to be able to replace the external segment without having to replace the entire system, thereby obviating pump exchange for driveline damage on the Controller side of the inline connector.
- Where appropriate, blood contacting surfaces have been texturized to prevent the formation of clots.

Please refer to the IFU for further information on the safety features of the HM3 LVAS.

Investigator Selection and Training:

It is also stated in the IFU that the devices can only be used by physicians who have received appropriate training on the proper use of the device. This statement is interpreted to mean that the physician users must complete Sponsor-provided HM3 training prior to clinical use and are expected to be aware of the known and foreseeable safety risks associated with the use of the devices including the surgical and/or non-surgical treatment of these conditions. Emergency surgical back-up should be available as per the institution's standard procedures. Cases may be supported by Abbott field personnel.

Ensuring Strict Adherence to the PMS plan

This confidential document is the property of Abbott and shall not be reproduced, distributed, disclosed or used without the express written consent of Abbott

Post Market Surveillance Plan

The post market surveillance will be carefully monitored by the Sponsor monitor (or designee) to ensure adherence to the PMS plan. Adverse events and device deficiencies will be reported to the Sponsor/designee and will be monitored internally for safety surveillance purposes.

Study Participation Risk Mitigation

Subject risk from participation will be mitigated by ensuring that only experienced LVAD personnel will be involved in the care of research subjects. In addition to providing local product specific IFU, staff involved in this post market surveillance study will have undergone product and PMS plan training prior to initiating study-related activities, and all subjects will be closely monitored throughout the surveillance period at pre-specified time points to assess their clinical status.

Specific information applicable to this PMS are listed below.

- It is suggested that patients possess a minimum 5th grade educational level.
- All users, including clinicians, patients, and caregivers, will be trained on HM3 system operation and safety before use.
- Clinical procedures, including adjustments to LVAS settings, should be conducted under the direction of the prescribing physician (Authorized Personnel) only.

15.6 Risk to Benefit Rationale

Participation in this post market surveillance study does not have any additional benefits or risks beyond what a patient may otherwise experience with the approved HM3 LVAS. However, this PMS will allow the collection of country specific data to incorporate within the continuing Risk Management activities of the Sponsor.

Post Market Surveillance Plan

APPENDIX I: ABBREVIATIONS AND ACRONYMS

Abbreviation	Term
ACEi	Angiotensin Converting Enzyme inhibitor
AE	Adverse Event
AI	Aortic Insufficiency
ALT	Alanine Aminotransferase
ARB	Angiotensin II Receptor Blockers
AST	Aspartate Aminotransferase
BTC	Bridge-to-Candidacy
BTT	Bridge-to-Transplant
CABG	Coronary Artery Bypass Graft
CI	Cardiac Index
CK	Creatinine Kinase
CK-MB	Creatinine Kinase Muscle/Brain
CNS	Central Nervous System
CO	Cardiac Output
CPB	Cardiopulmonary Bypass
CRF	Case Report Form
CT	Computed Tomography
CVP	Central Venous Pressure
DMP	Data Management Plan
DT	Destination Therapy
EDC	Electronic Data Capture
EPPY	Events Per Patient Year
eGFR	Estimated Glomerular Filtration Rate
FDA	Food and Drug Administration
GI	Gastrointestinal
HIE	Hypoxic-ischemic injury
HM3	HeartMate 3
ICF	Informed Consent Form
ICH	Intracranial Hemorrhage
IFU	Instructions for Use
INR	International Normalized Ratio
INTERMACS	Interagency Registry for Mechanically Assisted Circulatory Support
IRB	Institutional Review Board
LA	Left Atrium
LAA	Left Atrial Appendage
LDH	Lactate dehydrogenase

This confidential document is the property of Abbott and shall not be reproduced, distributed, disclosed or used without the express written consent of Abbott

Post Market Surveillance Plan

Abbreviation	Term
LV	Left Ventricle
LVAD	Left Ventricular Assist Device
LVAS	Left Ventricular Assist System
LVEDD	Left Ventricular End Diastolic Diameter
LVEF	Left Ventricular Ejection Fraction
LVESD	Left Ventricular End Systolic Diameter
MCS	Mechanical Circulatory Support
MCSD	Mechanical Circulatory Support Device
MI	Myocardial Infarction
MOMENTUM3	Multi-center Study of MagLev Technology in Patients Undergoing MCS Therapy With HeartMate 3™ IDE Study
MR	Mitral Regurgitation
MRI	Magnetic Resonance Imaging
MRS	Modified Rankin Score
MFDS	Ministry of Food and Drug Safety
NYHA	New York Heart Association
PAD	Diastolic Pulmonary Artery Pressure
PAS	Systolic Pulmonary Artery Pressure
PAM	Mean Pulmonary Artery Pressure
PMS	Post Market Surveillance
PR	Pulmonary Regurgitation
PRBC	Packed Red Blood Cells
PCWP	Pulmonary Capillary Wedge Pressure
RAP	Right Atrial Pressure
RHF	Right Heart Failure
RVAD	Right Ventricular Assist Device
SAE	Serious Adverse Event
SOC	Standard of Care
TE	Thromboembolism
tPA	Tissue Plasminogen Activator
TR	Tricuspid Regurgitation
UNOS	United Network for Organ Sharing
VAD	Ventricular Assist Device
VT	Ventricular Tachycardia

APPENDIX II: DEFINITIONS

ADVERSE EVENTS

1. Bleeding

An episode of SUSPECTED INTERNAL OR EXTERNAL BLEEDING that results in one or more of the following:

- a. Death,
- b. Reoperation,
- c. Hospitalization,
- d. Transfusion of red blood cells as follows:
 - If transfusion is selected, then apply the following rules:

During first 7 days Post-implant

- ≥ 50 kg: ≥ 4U packed red blood cells (PRBC) within any 24 hour period during first 7 days post-implant.
- <50 kg: ≥20 cc/kg packed red blood cells (PRBC) within any 24 hour period during the first 7 days post-implant

After 7 days Post-implant*

- Any transfusion of packed red blood cells (PRBC) after 7 days following implant with the investigator recording the number of units given. (Record number of units given per 24 hour period).

Note: Hemorrhagic stroke is considered a neurological event and not as a separate bleeding event.

*Any transfusion of ≥ 2U packed red blood cells (PRBC) after 7 days following implant will be considered a serious bleed

2. Cardiac Arrhythmias

Any documented arrhythmia that results in clinical compromise (e.g., diminished VAD flow, oliguria, pre-syncope or syncope) that requires hospitalization or occurs during a hospital stay. Cardiac arrhythmias are classified as 1 of 2 types:

- 1) Sustained ventricular arrhythmia requiring defibrillation or cardioversion.
- 2) Sustained supraventricular arrhythmia requiring drug treatment or cardioversion.

3. Pericardial Fluid Collection

Accumulation of fluid or clot in the pericardial space that requires surgical intervention or percutaneous catheter drainage. This event will be subdivided into those with clinical signs of tamponade (e.g. increased central venous pressure and decreased cardiac/VAD output) and those without signs of tamponade.

4. Device Thrombosis

Device thrombosis is an event in which the pump or its conduits contain a thrombus that results in or could potentially induce circulatory failure. Suspected device thrombus is an event in which

This confidential document is the property of Abbott and shall not be reproduced, distributed, disclosed or used without the express written consent of Abbott

Post Market Surveillance Plan

clinical or MCSD parameters suggest thrombus on the blood contacting components of the pump, cannulae, or grafts. Signs and symptoms should include at least 2 of the 3 following criteria:

- Presence of hemolysis
- Worsening heart failure or inability to decompress the left ventricle
- Abnormal pump parameters

Suspected pump thrombus should be accompanied by 1 or more of the following events or interventions:

- Treatment with intravenous anticoagulation (e.g., heparin), intravenous thrombolytics (e.g., tPA), or intravenous antiplatelet therapy (e.g., eptifibatide, tirofiban)
- Pump replacement
- Pump explant
- Urgent transplant (UNOS status 1A)
- Stroke
- Arterial non-CNS thromboembolism
- Death

Confirmed device thrombus is an event in which thrombus is confirmed by Abbott returned product analysis to be found within the blood contacting surfaces of device inflow cannula or outflow conduit or grafts. This can also be reported via direct visual inspection or by incontrovertible contrast radiographic evidence or by the absence of an appropriate Doppler flow signal that results in or could potentially induce circulatory failure or result in thromboembolism.

5. Hemolysis*

A plasma-free hemoglobin value that is greater than 40 mg/dl, concomitant with a rise in serum LDH above three times the upper limit of normal, in association with clinical signs associated with hemolysis (e.g., anemia, low hematocrit, hyperbilirubinemia) occurring after the first 72 hours post-implant.

*Hemolysis in the presence of worsening heart failure or inability to decompress the left ventricle or abnormal pump parameters should be reported as suspected device thrombosis, not as hemolysis

6. Hepatic Dysfunction

An increase in any two of the following hepatic laboratory values (total bilirubin, aspartate aminotransferase/AST and alanine aminotransferase/ALT) to a level greater than three times the upper limit of normal for the hospital, beyond 14 days post-implant (or if hepatic dysfunction is the primary cause of death).

7. Hypertension

Blood pressure elevation of a mean arterial pressure greater than 110 mm Hg, despite anti-hypertensive therapy.

This confidential document is the property of Abbott and shall not be reproduced, distributed, disclosed or used without the express written consent of Abbott

Post Market Surveillance Plan

8. Major Infection

A clinical infection accompanied by pain, fever, drainage and/or leukocytosis that is treated by anti-microbial agents (non-prophylactic). A positive culture from the infected site or organ should be present unless strong clinical evidence indicates the need for treatment despite negative cultures. The general categories of infection are listed below:

Localized Non-Device Infection

Infection localized to any organ system or region (e.g. mediastinitis) without evidence of systemic involvement (see sepsis definition), ascertained by standard clinical methods and either associated with evidence of bacterial, viral, fungal or protozoal infection, and/or requiring empirical treatment.

Percutaneous Site and/or Pocket Infection

A positive culture from the skin and/or tissue surrounding the drive line or from the tissue surrounding the external housing of a pump implanted within the body, coupled with the need to treat with antimicrobial therapy, when there is clinical evidence of infection such as pain, fever, drainage, or leukocytosis.

Internal Pump Component, Inflow or Outflow Tract Infection

Infection of blood-contacting surfaces of the LVAD documented by positive site culture.

Sepsis

Evidence of systemic involvement by infection, manifested by positive blood cultures and/or hypotension.

9. Myocardial Infarction

Two categories of myocardial infarction will be identified:

Peri-Operative Myocardial Infarction

The clinical suspicion of myocardial infarction together with CK-MB or Troponin > 10 times the local hospital upper limits of normal, found within 7 days following VAD implant together with ECG findings consistent with acute myocardial infarction. (This definition uses the higher suggested limit for serum markers due to apical coring at the time of VAD placement, and does not use wall motion changes because the apical sewing ring inherently creates new wall motion abnormalities.)

Non-Perioperative Myocardial Infarction

The presence at > 7 days post-implant of two of the following three criteria:

- a) Chest pain which is characteristic of myocardial ischemia,
- b) ECG with a pattern or changes consistent with a myocardial infarction, and
- c) Troponin or CK (measured by standard clinical pathology/laboratory medicine methods) greater than the normal range for the local hospital with positive MB fraction ($\geq 3\%$ total CK).

Post Market Surveillance Plan

This should be accompanied by a new regional LV or RV wall motion abnormality on a myocardial imaging study.

10. Neurologic Dysfunction

Any new, temporary or permanent, focal or global neurological deficit, ascertained by a standard neurological history and examination administered by a neurologist or other qualified physician and documented with appropriate diagnostic tests and consultation note; or an abnormality identified by surveillance neuroimaging. The examining physician will classify the event as defined below:

- Transient ischemic attack*, defined as an acute transient neurological deficit conforming anatomically to arterial distribution cerebral ischemia, which resolves in < 24 hours and is associated with no infarction on brain imaging (head CT performed >24 hours after symptom onset; or MRI)
- Ischemic Stroke*: a new acute neurologic deficit of any duration associated with acute infarction on imaging corresponding anatomically to the clinical deficit, or a clinically covert ischemic stroke seen by surveillance imaging, without clinical findings of stroke or at the time of event recognition.
- Hemorrhagic Stroke*: a new acute neurologic deficit attributable to intracranial hemorrhage (ICH), or a clinically covert ICH seen by surveillance imaging, without clinical findings of ICH at the time of event recognition.
- Encephalopathy: Acute new encephalopathy** due to hypoxic-ischemic injury (HIE), or other causes, manifest as clinically evident signs or symptoms, or subclinical electrographic seizures found by complete neurological diagnostic evaluation to be attributable to acute global or focal hypoxic, or ischemic brain injury not meeting one of ischemic stroke or ICH events as defined above.
- Seizure of any kind
- Other neurological event (non-CNS event): examples include neuro muscular dysfunction or critical care neuropathy

*Modified Rankin Score will be used to classify the severity of all strokes

**Acute encephalopathy is a sign or symptom of some underlying cerebral disorder and is manifest as depressed consciousness with or without any associated new global or multifocal neurologic deficits in cranial nerve, motor, sensory, reflexes and cerebellar function.

11. Psychiatric Episode

Disturbance in thinking, emotion or behavior that causes substantial impairment in functioning or marked subjective distress requiring intervention. Intervention is the addition of new psychiatric medication or hospitalization. Suicide is included in this definition.

12. Renal Dysfunction

Two categories of renal dysfunction will be identified:

This confidential document is the property of Abbott and shall not be reproduced, distributed, disclosed or used without the express written consent of Abbott

Post Market Surveillance Plan

Acute Renal Dysfunction

Abnormal kidney function requiring dialysis (including hemofiltration) in Subjects who did not require this procedure prior to implant, or a rise in serum creatinine of greater than 3 times baseline or greater than 5 mg/dL sustained for over 48 hours.

Chronic Renal Dysfunction

An increase in serum creatinine of 2 mg/dl or greater above baseline, or requirement for hemodialysis sustained for at least 90 days.

13. Respiratory Failure

Impairment of respiratory function requiring reintubation, tracheostomy or (the inability to discontinue ventilatory support within six days (144 hours) post-VAD implant. This excludes intubation for reoperation or temporary intubation for diagnostic or therapeutic procedures.

14. Right Heart Failure

Symptoms and signs of persistent right ventricular dysfunction requiring RVAD implantation or requiring inhaled nitric oxide or inotropic therapy for a duration of more than 1 week at any time after LVAD implantation.

15. Arterial Non-CNS Thromboembolism

An acute systemic arterial perfusion deficit in any non-cerebrovascular organ system due to thromboembolism confirmed by one or more of the following:

- Standard clinical and laboratory testing
- Operative findings
- Autopsy findings

This definition excludes neurological events.

16. Venous Thromboembolism Event

Evidence of venous thromboembolic event (e.g. deep vein thrombosis, pulmonary embolism) by standard clinical and laboratory testing.

17. Wound Dehiscence

Disruption of the exposed surfaces of a surgical incision, excluding infectious etiology, and requiring surgical repair.

18. Other

An event that causes clinically relevant changes in the Subject's health (e.g. cancer).

Post Market Surveillance Plan

MODIFIED RANKIN SCORE

Score	Definition
0	No observed neurological symptoms
1	No significant neurological disability despite symptoms; able to carry out all usual duties and activities
2	Slight neurological disability; unable to carry out all previous activities, but able to look after own affairs without assistance
3	Moderate neurological disability; requiring some help, but able to walk without assistance
4	Moderate severe neurological disability; unable to walk without assistance and unable to attend to own bodily needs without assistance
5	Severe neurological disability; bedridden, incontinent and requiring constant nursing care and attention as a result of a neurological deficit
6	Death

Post Market Surveillance Plan

DEVICE MALFUNCTIONS

A Device Malfunction occurs when any component of the MCS system ceased to operate to its designated performance specifications or otherwise fails to perform as intended. Performance specifications include all claims made in the Instructions for Use.

Internal Component Malfunction: Malfunction of any device system component that is implanted within the patient. A malfunction to these components may require further surgery to repair or replace.

External Component Malfunction: Malfunction of a device system component that is used external to the patient and can be replaced or repaired without the need for further surgery.

Post Market Surveillance Plan

NEW YORK HEART ASSOCIATION (NYHA) CLASSIFICATION

NYHA Classification	Definition
I	Cardiac disease without resulting limitations of physical activity. Ordinary physical activity does not cause undue fatigue, palpitations, dyspnea or anginal pain.
II	Cardiac disease resulting in slight limitation of physical activity. Subjects are comfortable at rest. Ordinary physical activity results in fatigue, palpitation, dyspnea or anginal pain.
IIIA	Cardiac disease resulting in marked limitations of physical activity. Subjects are comfortable at rest. Less than ordinary physical activity causes fatigue, palpitation, dyspnea, or anginal pain.
IIIB	Cardiac disease resulting in marked limitations of physical activity. Subjects are comfortable at rest. Mild physical activity causes fatigue, palpitation, dyspnea, or anginal pain.
IV*	Cardiac disease resulting in inability to carry on any physical activity without discomfort. Symptoms of cardiac insufficiency or of the anginal syndrome may be present even at rest. If any physical activity is undertaken, discomfort is increased.

*For all post-enrollment NYHA assessments, any patient who is inotrope dependent will be considered NYHA Class IV.

Post Market Surveillance Plan

INTERMACS PROFILE

INTERMACS Profile*	Definition
1	Critical cardiogenic shock describes a patient who is “crashing and burning”, in which a patient has life-threatening hypotension and rapidly escalating inotropic pressor support, with critical organ hypoperfusion often confirmed by worsening acidosis and lactate levels.
2	Progressive decline describes a patient who has been demonstrated “dependent” on inotropic support but nonetheless shows signs of continuing deterioration in nutrition, renal function, fluid retention, or other major status indicator. Patient profile 2 can also describe a patient with refractory volume overload, perhaps with evidence of impaired perfusion, in whom inotropic infusions cannot be maintained due to tachyarrhythmias, clinical ischemia, or other intolerance.
3	Stable but inotrope dependent describes a patient who is clinically stable on mild-moderate doses of intravenous inotropes (or has a temporary circulatory support device) after repeated documentation of failure to wean without symptomatic hypotension, worsening symptoms, or progressive organ dysfunction (usually renal). It is critical to monitor nutrition, renal function, fluid balance, and overall status carefully in order to distinguish between a patient who is truly stable at Patient Profile 3 and a patient who has unappreciated decline rendering this person a Patient Profile 2. This patient may be either at home or in the hospital.
4	Resting symptoms describes a patient who is at home on oral therapy but frequently has symptoms of congestion at rest or with ADL. He or she may have orthopnea, shortness of breath during ADL such as dressing or bathing, gastrointestinal symptoms (abdominal discomfort, nausea, poor appetite), disabling ascites or severe lower extremity edema. This patient should be carefully considered for more intensive management and surveillance programs, by which some may be recognized to have poor compliance that would compromise outcomes with any therapy.
5	Exertion Intolerant describes a patient who is comfortable at rest but unable to engage in any activity, living predominantly within the house or housebound. This patient has no congestive symptoms, but may have chronically elevated volume status, frequently with renal dysfunction, and may be characterized as exercise intolerant.
6	Exertion Limited also describes a patient who is comfortable at rest without evidence of fluid overload, but who is able to do some mild activity. Activities of daily living are comfortable and minor activities outside the home such as visiting friends or going to a restaurant can be performed, but fatigue results within a few minutes of any meaningful physical exertion. This patient has occasional episodes of worsening symptoms and is likely to have had a hospitalization for heart failure within the past year.
7	Advanced NYHA Class 3 describes a patient who is clinically stable with a reasonable level of comfortable activity, despite history of previous decompensation that is not recent. This patient is usually able to walk more than a block. Any decompensation requiring intravenous diuretics or hospitalization within the previous month should make this person a Patient Profile 6 or lower.

Post Market Surveillance Plan

6-MINUTE WALK TEST

Purpose

The purpose of the 6-Minute Hallway Walk test (6MWT) is to walk as far as possible for 6-minutes, without running or jogging, as a way of measuring functional status.

Preparing for the test

1. Establish a 30-meter walking course in an enclosed corridor, preferably free of distractions and close to a wall so that if needed, the Subject may rest against it during the test (note: a treadmill is not an acceptable alternate method for this PMS).
2. Mark the course at 3-meter intervals using a method unnoticeable to the Subject.
3. Place noticeable markers at either end of the 30-meter course to indicate the turnaround points.
4. The distance covered during the preceding walk test will not be revealed to the Subject during the PMS.
5. A warm up prior to the test should not be performed.

Explaining the test procedure to the Subject

1. Clearly explain to the Subject what is required of him/her using the following instructions verbatim:

THE PURPOSE OF THIS TEST IS TO WALK AS FAR AS POSSIBLE FOR SIX-MINUTES. YOU WILL START FROM THIS POINT AND FOLLOW THE HALLWAY TO THE MARKER AT THE END, THEN TURN AROUND AND WALK BACK. WHEN YOU ARRIVE BACK AT THE STARTING POINT, YOU WILL GO BACK AND FORTH AGAIN. YOU WILL GO BACK AND FORTH AS MANY TIMES AS YOU CAN IN THE SIX-MINUTE PERIOD. IF YOU NEED TO, YOU ARE PERMITTED TO SLOW DOWN, TO STOP, AND TO REST AS NECESSARY. YOU MAY LEAN AGAINST THE WALL WHILE RESTING, BUT RESUME WALKING AS SOON AS YOU ARE ABLE. HOWEVER, THE MOST IMPORTANT THING ABOUT THE TEST IS THAT YOU COVER AS MUCH GROUND AS YOU POSSIBLY CAN DURING THE SIX MINUTES. I WILL KEEP TRACK OF THE NUMBER OF LAPS YOU COMPLETE AND I WILL LET YOU KNOW WHEN THE SIX MINUTES ARE UP. WHEN I SAY STOP, PLEASE STAND RIGHT WHERE YOU ARE.

DO YOU HAVE ANY QUESTIONS ABOUT THE TEST?

PLEASE EXPLAIN TO ME WHAT YOU ARE GOING TO DO.

2. The Subject will re-state the instructions. If the Subject does not seem to understand, repeat the entire instructions.

Conducting the test

1. Position the Subject at the starting line.
2. Repeat the sentence:

THE MOST IMPORTANT THING ABOUT THE TEST IS THAT YOU COVER AS MUCH GROUND AS YOU POSSIBLY CAN DURING THE SIX MINUTES.

ARE YOU READY?

START NOW, OR WHENEVER YOU ARE READY.

3. Start the timer as soon as the Subject takes the first step.

This confidential document is the property of Abbott and shall not be reproduced, distributed, disclosed or used without the express written consent of Abbott

Post Market Surveillance Plan

4. During the test, the walking pace of the Subject should not be influenced. The test supervisor must walk behind the Subject – do not walk with, rush up behind, or rush past the Subject.
5. Each time the Subject returns to the starting line, record the lap.
6. While walking, encourage the Subject at one-minute intervals with the following phrases:

1 minute: YOU ARE DOING WELL. YOU HAVE 5 MINUTES TO GO.
2 minutes: KEEP UP THE GOOD WORK. YOU HAVE 4 MINUTES TO GO.
3 minutes: YOU ARE DOING WELL. YOU ARE HALFWAY DONE.
4 minutes: KEEP UP THE GOOD WORK. YOU HAVE ONLY 2 MINUTES LEFT.
5 minutes: YOU ARE DOING WELL. YOU HAVE ONLY ONE MINUTE TO GO.

7. The Subject should be spoken to only during the 1-minute encouragements; no response should be made to the Subject's questions about the time and distance elapsed.
 - a. If the Subject is not concentrating on the walking, the Subject can be reminded at a 1-minute mark:

THIS IS A WALKING TEST, TALKING WILL UTILIZE YOUR ENERGY RESERVE AND INTERFERE WITH YOUR PERFORMANCE.

When only 15 seconds remain, state:

IN A MOMENT I AM GOING TO TELL YOU TO STOP. WHEN I DO, STOP RIGHT WHERE YOU ARE AND I WILL COME TO YOU.

8. When the timer reads 6-minutes, instruct the Subject to STOP and walk over to him/her. Consider bringing a chair if the Subject appears exhausted. Mark the spot where the Subject stopped.

If the Subject wishes to stop walking during the test

If the Subject is slowing down and expresses that he/she wants to pause, keep the timer running and state:

REMEMBER, IF YOU NEED TO, YOU MAY LEAN AGAINST THE WALL UNTIL YOU CAN CONTINUE WALKING AGAIN.

If the Subject wishes to stop before the 6-minutes are complete and refuses to continue (or you decide that he/she should not continue), provide a chair for the Subject to sit on and discontinue the test. Record the distance completed, the time the test was stopped and the reason for prematurely stopping.

Immediately after the test

1. Total the number of completed laps and add the additional distance covered in the final partial lap. Record the distance walked to the nearest meter.
2. Observe the Subject sitting in a chair for at least 10 minutes after the test is completed.

Post Market Surveillance Plan

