8.2.2 Primary Safety Endpoint

Primary safety endpoint is measured by all pre-defined adverse events. Cumulative occurrence of adverse events during the surveillance period will be presented as percent of patients with adverse events and events per patient year of support.

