#### 1.4.2 Primary Safety Endpoint

Primary safety endpoint is measured by the cumulative occurrence of all adverse events defined in Appendix II of the CIP.

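### Right heart failure treated with drugs alone that is fatal within a week is missing from the right heart failure row of the primary safety endpoint; for respiratory failure the wording is only ambiguous

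*Protocol*

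**What the plan says.** Both documents build the primary safety endpoint on the Appendix II definitions. Protocol 8.2.2: "Primary safety endpoint is measured by all pre-defined adverse events". SAP 1.4.2: "Primary safety endpoint is measured by the cumulative occurrence of all adverse events defined in Appendix II of the CIP". SAP 2.2.4 reports each category as the percent of subjects affected and as events per patient-year.

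Two Appendix II items matter here.

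- **Item 14, Right Heart Failure**, has two routes. The first is "Symptoms and signs of persistent right ventricular dysfunction requiring RVAD implantation", with no minimum duration. The second is drug therapy: "requiring inhaled nitric oxide or inotropic therapy for a duration of more than 1 week at any time after LVAD implantation".
- **Item 13, Respiratory Failure**, has routes without a time limit, "Impairment of respiratory function requiring reintubation, tracheostomy", and one with a limit: "the inability to discontinue ventilatory support within six days (144 hours) post-VAD implant".

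Neither item mentions death. Two other items do. Item 6, Hepatic Dysfunction, has a 14-day limit but adds "or if hepatic dysfunction is the primary cause of death". Item 1, Bleeding, lists death among its qualifying results.

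Protocol 2.1 states that the Appendix II definitions are those of INTERMACS as used in MOMENTUM 3. Protocol 7.3.1 has the cause of every death during follow-up recorded.

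**The concern.** A category defined by how long treatment lasted can miss the patients in whom the condition was worst, because they did not live long enough to meet the duration. The loss runs one way. A fatal early course leaves the row unchanged, while a course survived past the threshold adds to it. A reader who takes the right heart failure row as a measure of how often the condition occurred would see a figure that is at or below the true one, with any shortfall made up of fatal cases.

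The category is a common one. Appendix IV gives 34.2% for right heart failure with the HeartMate 3 in MOMENTUM 3, and 21.6% for respiratory failure.

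**Working it through.** The plan states no figure on this point, so there is nothing to reproduce. The check is to apply the definitions to test cases and then scale the result.

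**Case A: right heart failure.** An implanted subject receives inotropes or inhaled nitric oxide, has no RVAD, and dies of right heart failure on day 4 of therapy.

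- RVAD route: not met.
- Drug route: 4 days is not more than 1 week, so not met.
- Item 14 has no third route, so the subject is not in the numerator.
- Denominator: Protocol 8.1 analyses all enrolled subjects and SAP 2.1 those with an HM3 implant. The subject is included under either.
- The limit is on duration of therapy and applies at any time after implant, so the same holds for a late episode that is fatal within a week of starting treatment.

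**Case B: respiratory failure.** A subject is ventilated from implant and dies of respiratory failure on day 3 (72 hours), with no reintubation or tracheostomy.

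- Reading 1: the subject never came off the ventilator in the six days, so the event counts.
- Reading 2: 144 hours were not reached, so inability was never shown and the event does not count.
- Neither document chooses between these, so sites may code the same course differently.

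**Where these deaths still appear.**

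- As primary efficacy events (Protocol 8.2.1, SAP 1.4.1).
- In the recorded causes of death (Protocol 7.3.1).
- Possibly under Appendix II item 18, the residual category.

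No text directs any of these into the right heart failure or respiratory failure row.

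**Scale.** Inputs: about 30 subjects (Protocol 5.6); 34.2% and 21.6% (Appendix IV), used only to set a plausible starting count. The number of uncounted deaths, m, is not in the documents. The values 0 to 2 are an assumption.

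- Change in the category percentage per uncounted subject: 1/30 = 3.3 points; for two, 2/30 = 6.7 points.
- Right heart failure: 30 × 0.342 = 10.3, so start from 10. Respiratory failure: 30 × 0.216 = 6.5; the illustration starts from 6.

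| m (assumed) | Right heart failure (exact 95% interval) | Respiratory failure (exact 95% interval) |
|---|---|---|
| 0 | 10/30 = 33.3% (17.3 to 52.8) | 6/30 = 20.0% (7.7 to 38.6) |
| 1 | 11/30 = 36.7% (19.9 to 56.1) | 7/30 = 23.3% (9.9 to 42.3) |
| 2 | 12/30 = 40.0% (22.7 to 59.4) | 8/30 = 26.7% (12.3 to 45.9) |

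- Events per patient-year: full two-year support in all subjects would give 30 × 2 = 60 patient-years. Each uncounted event therefore lowers the rate by about 1/60 = 0.017, and by more when total support time is shorter.

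**The case against.** The strongest reply is that these definitions were adopted, not drafted for this study. Protocol 2.1 says so, and Appendix IV gives MOMENTUM 3 rates for both categories. Rewriting items 13 and 14 would take the main figures off that basis. This stands, and it is why the definitions should be left alone.

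Second, a reader might infer that these subjects drop out of the safety results altogether. The documents do not support that. The deaths are efficacy events with a recorded cause, and item 18 is itself part of Appendix II, so the event can enter the primary safety endpoint under that heading. What is lost is the label. It is still a loss for anyone reading the right heart failure row, because a fatal right heart failure filed under a residual heading is hard to find.

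Third, a reader might infer that a ventilator death before 144 hours is definitely excluded from respiratory failure. The wording does not settle that, as Case B shows.

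Fourth, the hepatic clause might be read as proof that the authors saw this problem and forgot to carry the remedy over. The documents give no reason for the clause, and its limit is on time since implant, not on duration of therapy. Other time-limited items (hemolysis, chronic renal dysfunction, and the sustained-creatinine route of acute renal dysfunction) have no death clause either. The hepatic and bleeding items show only that counting death is compatible with the style of the appendix.

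Finally, the effect is small beside the sampling error. One subject is 3.3 points, against an interval of 17.3 to 52.8% for 10/30. No endpoint is powered (note to SAP 1.4.3) and there is no success criterion (SAP 2.6). This stands, and it makes the point one of clear reporting, with no decision resting on it.

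**Conclusion.** The point holds in a limited form. Under item 14, a subject on drug therapy alone who dies of right heart failure within the week cannot be counted in that row, and no other text puts the death there. For item 13 there is an ambiguity, not an established exclusion.

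The direction is certain: the right heart failure row can only be understated. The size is unknown. It is 3.3 percentage points per subject at about 30 subjects, and zero if no such death occurs. Any total, such as 6.7 points for two deaths, rests on an assumed count. The 34.2% from MOMENTUM 3 does not help to estimate that count, because Protocol 2.1 indicates that it was obtained under the same definition. It shows only that the category is common.

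This is a modest reporting improvement. It does not call for rewriting the definitions.

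**What to change.** Leave Appendix II items 13 and 14 as they are and use them for the main row of each category. In SAP 2.2.4 (body numbering):

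1. Add a second right heart failure row, in percent of subjects and events per patient-year, that also counts subjects whose recorded primary cause of death is right heart failure and who are not already in the main row.
2. State that a subject who dies of respiratory failure while still ventilated before 144 hours is handled in the same way for item 13: outside the main row and inside the second row. This also removes the scope for different coding between sites.

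The cost is one extra row per category and two sentences in the SAP. No new data should be needed, provided that the case report form identifies the primary cause of death. Protocol 7.3.1 has causes of death captured, but the forms are supplied separately. The second row will be slightly less favourable if any such death occurs. The main right heart failure row stays on the MOMENTUM 3 basis. For item 13 the documents do not say how MOMENTUM 3 coded early ventilator deaths, so a footnote should state the rule used here.
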